**Table 5. Study Measures**

Domain	Measures & Indicators	Interval
I. Client Measures: Effectiveness Outcomes		
Depression Severity	Patient Health Questionnaire-9 (PHQ-9; [name], Spitzer, & Williams, 2001). The PHQ-9 is a 9 item self-report that assesses depression severity and has demonstrated good internal consistency ( $\alpha=.85\text{-.89}$ ) and sensitivity to change (Löwe, [name], Herzog, & Gräfe, 2004).	All Sessions
II. Clinician Measures: Contextual Factors of the Diffusion Process (Putative Predictors, Moderators, & Mediators)		
Demographics	Developed by [name] & Simons (2011) to assess clinician demographic information and training background.	BL
Norms	A measure of subjective norms will be developed (3 items; Francis et al., 2004) in proposal Phase I and used to assess normative behavior per the theory of planned behavior measurement development manual.	BL, AT2, AT3
Attitudes	Attitudes Towards Standardized Assessment (ASA; Jensen-Doss & Hawley, 2010) is a 22-item self-report that assesses attitudes toward use of standardized assessments (e.g., PHQ-9). The ASA has good internal consistency ( $\alpha=.72\text{-.75}$ ) for each subscale (Benefit Over Clinical Judgment, Psychometric Quality, Practicality) and good structural validity.	BL, AT2, AT3
Culture/Climate	Organizational Culture Scale (Glaser, Zamanou, & Hacker, 1987) is a 31-item self-report that assesses organizational culture using a 5-point Likert scale for 6 factors: teamwork, morale, information flow, involvement, supervision, and meetings. The OCS has demonstrated strong inter-item reliability ( $\alpha=.98$ ) among the subscales.	BL, AT2, AT3

Structure/ Process Policies/ Incentives	Infrastructure Survey (Keough, Comtois, [name], & Landes, 2013) is a 30-item self-report that assesses the impact of infrastructure (e.g., documentation, performance evaluation, productivity requirements) of clinical settings on the implementation and sustainment of empirically supported treatments. Psychometrics will be available Fall 2014.	BL, AT2, AT3
Resources	Organizational Resources Scale (ORS; Salanova, Agut, & Peiró, 2005). is an 11-item self report that assesses organizational resources across subscales of Training, Autonomy, and Technology and has good internal consistency ( $\alpha=.84-.91$ ).	BL, AT2, AT3
Networks & Linkages	We will map the network within each clinic and calculate: the number of links connecting network members (density), and the number of direct connections to and from the opinion leader (centrality).	BL, AT2, AT3
Media & Change Agents	Opinion Leadership Scale (OLS; Childers, 1986). The OLS is a 6-item opinion leader self-identification scale that will be employed to identify clinician opinion leaders who may serve as change agents. The OLS has demonstrated good internal consistency ( $\alpha=.83$ ).	BL, AT2, AT3

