**Aim 1: Hypotheses:** Tailored implementation will outperform standardized in terms of (H1a) fidelity. MBC clinician fidelity was evaluated with two variables: (1) whether the PHQ-9 was recorded in the EHR, and (2) among encounters for which the PHQ-9 was recorded, whether it was discussed. Both outcomes were modeled using generalized linear mixed models with a logit link function for a binary distribution using the lme4 package. All models included random intercepts for clinicians and patients. Models for both outcomes were constructed in an identical sequence. Models comparisons in the model-building sequence described below were evaluated using the Bayesian Information Criterion (BIC); the model with the better BIC was selected for presentation. Several unconditional growth models (i.e., models with only parameters for time) were fit (i.e., linear, quadratic, log-transformed number of months). After establishing the unconditional growth model, additional fixed effects were added in the following sequence: (1) group main effect and (2) group x time interaction. Finally, new versus existing patient status was investigated as a main effect using a dummy variable for new patient status and as a patient status x group interaction.

**Aim 2: Hypotheses:** Contextual mediators will be leveraged in the tailored condition, but serve as barriers in the standardized condition. Mediation models were fit to evaluate which contextual factors (based on clinician-completed surveys, Table 5; and, clinician selection of drop-down menu reasons for MBC deviations captured in the electronic health record) mediate the impact of the implementation condition on both clinician- and client-level outcomes. The two critical effects underlying mediation were evaluated in separate models: treatment condition predicts the mediator (path *a*) and the mediator predicts the outcome (path *b*). Specifically, mediators were assessed at the conclusion of the implementation window and the mediators were used to predict PHQ9 completion in the sustainment window. The *a* path was assessed using linear mixed models with Satterthwaite degrees of freedom

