implemented using the R lmerTest package with a random intercept for clinic. The b path was assessed using generalized linear mixed models with a logit link function for a binary distribution using the lme4 package. **Aim 3 Hypotheses:** Adapted MBC protocols (i.e., tailored condition) will outperform routine weekly administration of PHQ-9s (i.e., standardized condition) with respect to clinically significant change in depression severity from intake to week 12. Depression severity was analyzed using linear mixed models with Satterthwaite degrees of freedom implemented using the R lmerTest package. Multiple imputation was used to estimate missing values across 20 datasets in which 22.8% of patients did not complete the 12-week interview. We first assessed whether there was a change in PHQ-9 between intake and week 12 in a mixed model containing patient status as a covariate and random intercepts for patient and clinic. Next, implementation group was added to the model. In addition, number of sessions, number of sessions that the PHQ-9 was recorded, and number of sessions that the PHQ-9 was discussed were added to the model. We also examined the interactions between new patient status and the focal variables. **Power calculations.** A power analysis for the multilevel models for Aim 1 was assessed with Monte Carlo studies in which power is the proportion of significant effects (2-tailed  $\alpha$ ,  $p < .05$ ) for parameters of interest observed over repeated analyses of simulated data (Muthén & Muthén, 2002; Thoemmes, Reiser, & MacKinnon, 2010) using MPlus (version 7). For each model, 10,000 data sets were simulated and analyzed. Data in the Monte Carlo studies were simulated with the goal of identifying the smallest detectable effect size with power  $> 80$ . Dropout was simulated to reflect an increase of 5% missing data per wave. Repeated measurements were nested within participants (ICC = .50) and participants were nested in sites (ICC = .05). Average effect sizes for Aim 1 analyses were computed using an approximation of Cohen's  $d$  for growth models (Feingold, 2009). Using this metric, we are sufficiently powered to detect effect sizes as small as  $d = .46$  for the clinician models ( $N = 150$ ) and effect sizes as small as  $d = .30$  for the client models ( $N = 500$ ). For Aim 2, we conducted power analyses for the hypothesized mediation effects with the same assumptions described above but with the use of effective samples size estimates (an ICC corrected sample size) based on a design effect adjustment (Bickel, 2007) in order to use standard effect size metrics. The  $\kappa^2$  effect size for mediation (.01, .09, and .25 represent small, medium, and large  $\kappa^2$  respectively) was computed (Preacher & Kelly, 2011). We are sufficiently powered to detect effect sizes as small as  $\kappa^2 = .16$  for the clinician models and effect sizes as small as  $\kappa^2 = .10$  for the client models. For Aim 3 analyses, we are sufficiently powered to detect effect sizes as small as  $r = .27$  for clinicians and as small as  $r = .21$  for clients. The planned sample sizes are consistently sufficient for detecting medium effect sizes for clinician outcomes and small effect sizes for client outcomes, with the power to treat site as a random effect based 6 sites per condition (Atkins & Baldwin, 2013).

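### Network density and opinion-leader centrality have one value per clinic, but Aim 2 gives no clinic-level mediator model: the stated path-a model is degenerate for them and path b's random effects are not stated

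*Combined protocol and SAP*

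**What the plan says.** Table 5, Section II is headed "Contextual Factors of the Diffusion Process (Putative Predictors, Moderators" and mediators. Its Networks & Linkages row says "We will map the network within each clinic and calculate" two quantities: "the number of links connecting network members (density), and the number of direct connections to and from the opinion leader (centrality". They are collected at baseline, 5 months and 15 months.

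C13a, Aim 2 fits mediation models to "evaluate which contextual factors (based on clinician-completed surveys, Table 5" and the reasons clinicians select for deviating from MBC. The two paths are fitted separately. For path a, the "path was assessed using linear mixed models with Satterthwaite degrees of freedom", "implemented using the R lmerTest package with a random intercept for clinic". Path b is a logit mixed model in lme4 that predicts PHQ-9 completion during sustainment from the mediator at the end of implementation; its random effects are not stated. The Aim 1 models, also logit mixed models of PHQ-9 recording, have clinician and patient intercepts and no clinic term. The power paragraph gives a detectable kappa-squared of .16 for clinician models and refers to treating site as random with 6 sites per condition.

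**The concern.** A score computed once per clinic is the same for every clinician there. Path a has that score as its response and a clinic random intercept as its random effect, so no within-clinic variation is left to estimate a residual variance. Path b has the score as its predictor; if no term in the model represents the clinic, 12 distinct values are tested as if they carried information from every clinician.

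H2 is a claim about contextual mediators, and networks and linkages is one of the named factors. For that factor the plan as written may yield no path-a result, or one with false precision, and a path-b test whose error rate depends on an unstated choice.

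**Working it through.** **Inputs.** 12 clinics, 6 per condition (C13a, power); 150 clinicians, so 12.5 per clinic; site ICC .05; two-sided alpha .05. Assumed for the path-b simulation: 3 patients per clinician, 8 encounters per patient, and the variances given below.

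**The plan's own figure.** The design effect is 1 + (12.5 − 1) × .05 = 1.575, so the effective N is 150/1.575 = 95. With equal paths and no direct effect (assumed), simulated power of 80% is reached at a kappa-squared of about .11 (joint significance) or .13 (Sobel), against .16 stated. The plan does not give the test, the split between paths or the direct effect, and a more conservative choice could give .16, so I do not call this an error. What matters here is that the figure rests on an effective N near 95, not on 12.

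**Path a, plan's package (lmerTest), no true effect.**
- 12 rows, one per clinic: lmer stops, because the grouping factor has as many levels as there are observations.
- 150 rows with clinic values repeated, 1,000 runs: 78% gave warnings and 25% gave no p-value. Among runs with a p-value, 25% were below .05.
- The median ratio of the reported SE to the correct clinic-level SE was 0.26 (10th to 90th percentile 0.23 to 0.28). The arithmetic agrees: as the residual variance goes to 0, the between-clinic sum of squares is divided by 150 − 2 = 148 instead of 12 − 2 = 10, and √(10/148) = 0.26.
- The Satterthwaite degrees of freedom had no stable meaning: 10th, 50th and 90th percentiles of 0.006, 0.02 and 348, against a correct value of 10.
- A two-sample t test on the 12 clinic values rejected in 5.8% of runs.

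**Path b, if Aim 1's intercepts are used with no clinic term.**
- Analytic type I error is 2{1 − Φ(1.96/√DE)}. With DE = 1.575 this is 2{1 − Φ(1.56)} = 11.8%.
- Simulation with glmer (400 runs, Monte Carlo error about 2 points; variances: site 0.329, clinician 2.961, patient 1): 19.5%. Here site holds 0.329/3.29 = 10% of site-plus-clinician variance, which is why the rate exceeds the analytic one.
- Same data with a clinic intercept added and a Wald z test: 12%. Even with a correct SE, a z test referred to 1.96 when 9 df are available rejects in 8.2%.
- A test on 12 clinic rows held 4.4% to 5.8% over site ICCs from 0 to .20.

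**What 12 values can detect (80% power).**
- Path a, 6 v 6 on 10 df: a difference of 1.80 between-site SDs.
- Path b: a correlation of .67 (noncentral t) or tanh(2.80/√9) = .73 (Fisher z). With condition in the regression, the partial correlation is tanh(2.80/√8) = .76.
- Both paths at .6, a kappa-squared of about .32: joint power is about 21%. At .16 it is lower still.

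**The case against.** - **The network scores may not enter as clinic-level mediators.** Aim 2 speaks of clinician-completed surveys, and Table 5 does not say which factor is a predictor, moderator or mediator. Section VII collects a sociometric questionnaire from each clinician, which could support individual scores, and allows 2-4 clinician leaders and champions on a team. This makes inclusion probable, not certain. But the questionnaire belongs to the clinician battery, no individual score is defined, and the scores that are defined are computed per clinic.
- **Path b may include a clinic term.** A reader might infer that path b certainly treats 12 values as many. The documents do not say so: path a has a clinic intercept and the power paragraph mentions random sites. The path-b figures without a clinic term are conditional on Aim 1's structure carrying over.
- **The path-a failure is mostly visible.** In lmerTest it usually shows as a warning, an error or a missing p-value. A fit in a different package (statsmodels) rejected 61% of the time, but the plan does not use that package. What stands is that the p-values lmerTest does return rest on a wrong SE.
- **Pilot data might suggest a larger site effect.** One could turn the pilot's 44% and 80% penetration into a site ICC of about .17 and a path-b error of 21%. The site denominators are not stated, there are only two sites, and C9 attributes part of Site A's shortfall to technology. I do not rely on it.
- **The stakes are limited.** Aim 2 is exploratory, two indices of one factor are affected, and Aim 1 is untouched. This stands and limits the weight of the point.

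**Conclusion.** The point holds for network density and opinion-leader centrality as Table 5 defines them. Path a as stated is degenerate: it fails, or returns an SE about 0.26 of the correct one, with about 25% false positives among the p-values that lmerTest returns. For path b the firm finding is that the random effects are unspecified. Without a clinic term the error is about 12% at an ICC of .05 (19.5% in one simulated setting), and a Wald z test with a clinic intercept still gave 12%. The stated kappa-squared of .16 does not apply to these mediators.

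A reader might go further and infer that false mediation findings will follow, or that these are the mediators most likely to be declared in error. The documents support neither. Mediation needs both paths, no rule for combining them is given, no joint error rate was computed, and no other mediator was compared. The supported conclusion is a raised risk of a spurious or missing result for one named factor in an exploratory aim.

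**What to change.** In C13a, Aim 2, add a paragraph for clinic-level mediators:

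- **Path a:** compare the 12 clinic values, 6 v 6 on about 10 df, or by an exact permutation test. Either should respect the matching on size and urban/rural status in C11. The pairing is not given; if there are six matched pairs, there are 2^6 = 64 allocations and the smallest two-sided p-value is 2/64 = .031.
- **Path b:** regress clinic-level PHQ-9 completion in sustainment on the mediator and condition, using the 12 clinic values.
- **Precision:** state that n=12 detects only very large effects (about 1.8 between-site SDs for path a, a correlation of about .7 for path b), that the kappa-squared of .16 does not cover these mediators, and that the results are descriptive.
- **Clinician-level mediators:** state path b's random effects and include a clinic random intercept.

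C13a is partly in the past tense, so any network result already produced should be checked against this. The cost is SAP wording and wider intervals for two exploratory mediators; no new data are needed.

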## **C12. Participants: Recruitment, Retention, and Data Collection Procedures**

### **C12a. Clinicians**

**Recruitment.** Participants will be recruited across 12 sites (Clinicians:  $N=187$ ; target:  $N=150$ ) (*Letter of Support*: CEO [name]). The number of sites and clinicians has been determined by a simulation-style power analysis to detect a small effect size predicted by previous research (*C13. Data Analysis Plan*). The main sites have been identified, but not enrolled (*Letters of Support* from regional clinic directors). As there are at least 16 sites from which to select (easily accessible from primary site) and at least 250 eligible clinicians across these sites, we are confident that we can obtain the targeted number of both sites and clinicians. Said differently, even if a site administrator enrolls a site, not all clinicians will need to participate, an important factor to avoid any perception of coercion. Given site diversity, the large number of eligible sites will maximize the likelihood that results will generalize to the broader population of community mental health centers. Sites range in size from 12 to 52 clinicians. Within each enrolled site, clinicians will have the option to participate if they (a) are at least 80% full-time equivalent (b) provide individual psychotherapy to (c) adults with depression (d) in English. These inclusion criteria reflect over 95% of clinicians at the eligible sites. Based on our pilot study, we have experienced that even those who are not supportive of MBC have agreed to participate, therefore making it unlikely that self-selection to participate would limit the generalizability of our sample. During Phase 1 (months 5-8; Table 4), clinician enrollment will begin across all sites and site randomization will occur as site level randomization improves project feasibility and reduces contamination confounds. This decision to randomize by site was also influenced by literature indicating the impact of organizational culture and climate on the implementation process (Aarons et al., 2012; Damschroder et al., 2009), which will be assessed at baseline (AT1).

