## **C. Number of Subjects.**

### **Clinicians**

Clinicians will be recruited from 12 Centerstone sites across two states (Indiana and Tennessee). Approximately 187 clinicians (average of 16 per site) will be recruited during the latter half of Phase 1 of the study (months 5 to 8) to achieve our target enrollment of 150 (accounting for clinician turnover) and allow for initial site randomization (to early or late and standardized or tailored implementation) to occur just prior to Phase 2 (months 8-38).

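### Table 5 scores network density as an undivided count of links, so the Aim 2 network measure rises with site size unless it is scaled

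*Combined protocol and SAP*

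**What the plan says.** Table 5, Section II, lists Networks & Linkages among the putative predictors, moderators and mediators, measured at BL, AT2 and AT3. One network is drawn per site ("We will map the network within each clinic and calculate"), and the two quantities taken from it are "the number of links connecting network members (density), and the number of direct connections to and from the opinion leader (centrality". Neither is divided by anything, here or elsewhere in the text.

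C12a says of site size: "Sites range in size from 12 to 52 clinicians". It describes a pool of at least 16 sites with "at least 250 eligible clinicians across these sites". Section V, Number of Subjects, states: "Approximately 187 clinicians (average of 16 per site) will be recruited".

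Aim 2 in C13a says "Mediation models were fit to evaluate which contextual factors (based on clinician-completed surveys, Table 5". Mediators taken at the end of active implementation predict PHQ-9 completion during sustainment. Path a (condition to mediator) is a linear mixed model "implemented using the R lmerTest package with a random intercept for clinic". Path b (mediator to completion) is a logit mixed model. Neither is said to adjust for site size. C11 matches sites on size and on urban or rural status before randomization.

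The network data come from a sociometric questionnaire (Section VII, Appendix A.11). Its nomination format and scoring are not in the text available. Section VII includes the same questionnaire in the shortened battery for general staff, so the text leaves open whether network members are clinicians only.

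**The concern.** Density normally means the share of possible ties that are present. The rule under that label is a count, and the number of ties that can exist grows roughly with the square of membership. An analyst who applies Table 5 as written gives a large site a high score and a small site a low one when both are equally connected.

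The score also moves with response. C12a does not require every clinician at a site to take part, and C12a (Retention) reports 11.72% clinician attrition in the preceding year. A site's count can therefore change between BL, AT2 and AT3 with no change in who talks to whom.

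At stake is the reading of one Aim 2 mediator domain. If PHQ-9 completion differs between large and small sites for any reason, an unscaled count entered in path b can pick up that difference and be reported as an effect of staff networks.

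**Working it through.** The documents give no computed value for either measure, so there is no figure to reproduce. The check works from the written definition and the stated site sizes.

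**1. Maximum scores.** For n members, possible directed links are n(n−1), and possible connections to and from one person are 2(n−1).

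| n | Source | n(n−1) | 2(n−1) |
|---|---|---|---|
| 12 | smallest site, C12a | 132 | 22 |
| 16 | planned average, Section V | 240 | 30 |
| 52 | largest site, C12a | 2,652 | 102 |

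From 12 to 52 the link maximum rises 2,652/132 = 20.1-fold and the opinion-leader maximum 102/22 = 4.6-fold. The ratios are the same for undirected ties.

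**2. Equal connectedness, unequal score.** If a quarter of possible links are present (assumption), the count is .25 × 132 = 33 at 12 clinicians and .25 × 2,652 = 663 at 52.

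**3. Response.** If respondents at a site fall from 16 to 13, the maximum goes from 240 to 13 × 12 = 156. Since 156/240 = .65, that is a 35% fall.

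**4. Capped nominations.** If each clinician names exactly five colleagues (assumption), links are 5 × 12 = 60 and 5 × 52 = 260, a 4.3-fold range. Density then runs the other way: 5/11 = .45 and 5/51 = .10. A cap shrinks the distortion in the count, but it also makes the usual density depend on size.

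**5. How far size dominates.** Twelve sites were simulated with true density of mean .25 and SD .05 to .10, unrelated to size, and uncapped directed ties (all assumptions).

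| Assumed sizes of the 12 sites | Correlation of count with size | Correlation of count with true density |
|---|---|---|
| 12–16 (SD .10) | .43 | .83 |
| 12–20, total 192 (SD .05 to .10) | .82 to .62 | .46 to .70 |
| Eleven of 12–16 and one of 52 | .98 to 1.0 | not needed for the point |

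**6. Effect of scaling.** A separate simulation used undirected ties and true connectedness of mean .3 (SD .05 to .15) or .5 (SD .20). Links divided by possible links had a median R² with size of .02 to .05 in every size mix, and .52 to .98 with true connectedness. The raw opinion-leader count had a median R² with size of .38 to .82 when sizes spanned 12 to 52, but only .07 to .09 when all sites held 12 to 16.

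**The case against.** **Shorthand.** C12a calls the Table 5 entries concise, and the label may stand for the usual proportion. That is possible, but the entry spells out a count and nothing corrects it.

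**Centrality.** A raw count of direct connections is a recognised degree measure, so that entry is not mislabelled. It also scales far less with size. This stands, and the point is mainly about density.

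**Path a.** Matching on size keeps the arms roughly comparable, so the condition effect on the mediator loses precision but is not biased. This stands too.

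**Stronger readings.** From the 12-to-52 range a reader might infer that the score measures site size rather than connectedness. The documents do not support that. Twelve sites spread evenly over that range would average (12 + 52)/2 = 32 clinicians and total 384, against 187 planned. The range appears in the description of the candidate pool, and the enrolled sizes are not given. At sizes of 12 to 20 with density SD .10, the count follows true density (.70) more closely than size (.62).

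A reader might also attach a false-positive rate to path b. With the even 12-to-52 spread it comes out at 29 to 38%. That figure rests on an assumed correlation of −.5 between site size and completion, which the documents do not give, and on a 12-point correlation test instead of the planned logit mixed model. At sizes of 12 to 20 the same exercise gives 17 to 28%. These rates largely return the assumption and should not be quoted as properties of the plan.

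**Scope.** Aim 2 is secondary and exploratory, two indicators in one domain are involved, and no primary outcome is affected. No passage names density individually as a fitted mediator; it enters through the general reference to Table 5.

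**Conclusion.** The concern holds for density. The written rule does not match its label, no denominator is given anywhere, and the Aim 2 models state no size adjustment. Across the stated range the maximum score varies 20-fold if nominations are uncapped, and 4.3-fold under a fixed five names.

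The practical size of the problem is open. Under the density assumptions above, the correlation of the count with site size is about .4 to .8 if all sites hold 12 to 20 clinicians. One 52-clinician site takes it to about .98 or more, because that site becomes a leverage point. Which case applies depends on enrolled sizes and on the questionnaire format.

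The exposure is chiefly in path b, and only to the extent that completion is in fact related to site size. The opinion-leader count is less affected (up to 4.6-fold) and is acceptable as a degree measure within a site. It needs scaling only for comparison across sites. The change is worth making because it is nearly free and otherwise the Networks & Linkages result could not be interpreted with confidence.

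**What to change.** In Table 5, and by reference in C13a Aim 2:

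- Define density as observed links divided by possible links among respondents at that time point, with n(n−1) possible links for directed ties. If the sociometric form caps the number of names, use mean ties per respondent instead.
- For comparison across sites, report opinion-leader centrality as incoming plus outgoing ties divided by 2(n−1).
- State who counts as a network member (clinicians only, or general staff as well) and how nonrespondents are handled at BL, AT2 and AT3.
- Report the enrolled site sizes next to the network scores.

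A site-size covariate alone is a weaker repair, because with one very large site the count and size are almost collinear and the model could not separate them.

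The cost is a few lines of text and a small change in code. The sociometric questionnaire already supplies the ties and n. Aim 2 is written in the past tense, so if the network models have been run on raw counts they should be rerun on the scaled scores.
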